## 6.2 Exclusion Criteria

### 1) Medical Conditions

- a) Subjects with known EGFR mutations which are sensitive to available targeted inhibitor therapy (including, but not limited to, deletions in exon 19 and exon 21 [L858R] substitution mutations) are excluded. All subjects with non-squamous histology must have been tested for EGFR mutation status; use of an FDA-approved test is strongly encouraged. Non-squamous subjects with unknown or indeterminate EGFR status are excluded.
- b) Subjects with known ALK translocations which are sensitive to available targeted inhibitor therapy are excluded. If tested, use of an FDA-approved test is strongly encouraged. Subjects with unknown or indeterminate ALK status may be enrolled.
- c) Subjects with untreated CNS metastases are excluded.
  - i) Subjects are eligible if CNS metastases are adequately treated and subjects are neurologically returned to baseline (except for residual signs or symptoms related to the CNS treatment) for at least 2 weeks prior to enrollment. In addition, participants must be either off corticosteroids, or on a stable or decreasing dose of  $\leq 10$  mg daily prednisone (or equivalent) for at least 2 weeks prior to treatment assignment.
- d) Prior malignancy active within the previous 3 years except for locally curable cancers that have been apparently cured, such as basal or squamous cell skin cancer, superficial bladder cancer, or carcinoma in situ of the prostate, cervix, or breast.
- e) Subjects with an active, known or suspected autoimmune disease. Subjects with type I diabetes mellitus, hypothyroidism only requiring hormone replacement, skin disorders (such as vitiligo, psoriasis, or alopecia) not requiring systemic treatment, or conditions not expected to recur in the absence of an external trigger are permitted to enroll.
- f) Subjects with a condition requiring systemic treatment with either corticosteroids ( $> 10$  mg daily prednisone equivalent) or other immunosuppressive medications within 14 days of

enrollment. Inhaled or topical steroids, and adrenal replacement steroid doses  $> 10$  mg daily prednisone equivalent, are permitted in the absence of active autoimmune disease.

- g) Subjects with interstitial lung disease that is symptomatic or may interfere with the detection or management of suspected drug-related pulmonary toxicity.
- h) Subjects with serious or uncontrolled medical disorders and any known medical condition that, in the investigator's opinion, would increase the risk associated with study participation or study drug administration or interfere with the interpretation of safety results.
- i) Subjects with a known history of a positive test for human immunodeficiency virus (HIV) or known acquired immunodeficiency syndrome (AIDS). NOTE: Testing for HIV must be performed at sites where mandated locally. See [Appendix 8](#).

## 2) Prior/Concomitant Therapy

- a) Prior treatment with an anti-PD-1, anti-PD-L1, anti-PD-L2, anti-CTLA-4 antibody, or any other antibody or drug specifically targeting T-cell co-stimulation or checkpoint pathways.
- b) Treatment with botanical preparations (eg herbal supplements or traditional Chinese medicines) intended for general health support or to treat the disease under study within 2 weeks prior to treatment.

## 3) Physical and Laboratory Test Findings

Screening laboratory values that meet the following criteria (using CTCAE v4):

- a) WBC  $< 2000/\mu\text{L}$
- b) Neutrophils  $< 1500/\mu\text{L}$
- c) Platelets  $< 100 \times 10^3/\mu\text{L}$
- d) Hemoglobin  $< 9.0 \text{ g/dL}$
- e) Serum creatinine  $> 1.5 \times \text{ULN}$ , unless creatinine clearance  $\geq 40 \text{ mL/min}$  (measured or calculated using the Cockcroft-Gault formula)  
$$\text{Female CrCl} = \frac{(140 - \text{age in years}) \times \text{weight in kg} \times 0.85}{72 \times \text{serum creatinine in mg/dL}}$$

$$\text{Male CrCl} = \frac{(140 - \text{age in years}) \times \text{weight in kg} \times 1.00}{72 \times \text{serum creatinine in mg/dL}}$$

- f) AST  $> 3.0 \times \text{ULN}$
- g) ALT  $> 3.0 \times \text{ULN}$
- h) Total Bilirubin  $> 1.5 \times \text{ULN}$  (except subjects with Gilbert Syndrome who must have a total bilirubin level of  $< 3.0 \times \text{ULN}$ ).
- i) Any positive test for hepatitis B virus or hepatitis C virus indicating presence of virus, e.g. Hepatitis B surface antigen (HBsAg, Australia antigen) positive, or hepatitis C antibody (anti-HCV) positive (except if HCV-RNA negative)

## 4) Allergies and Adverse Drug Reaction

- a) History of allergy or hypersensitivity to study drug components.

## 5) Other Exclusion Criteria

- a) Prisoners or participants who are involuntarily incarcerated. (Note: under certain specific circumstances a person who has been imprisoned may be included or permitted to continue as a participant. Strict conditions apply and Bristol-Myers Squibb approval is required.)
- b) Participants who are compulsorily detained for treatment of either a psychiatric or physical (e.g., infectious disease) illness

Eligibility criteria for this study have been carefully considered to ensure the safety of the study participants and that the results of the study can be used. It is imperative that participants fully meet all eligibility criteria.

## 6.3 Lifestyle Restrictions

Not applicable. No restrictions are required

## 6.4 Screen Failures

Screen failures are defined as participants who consent to participate in the clinical study but are not subsequently registered for treatment. A minimal set of screen failure information is required to ensure transparent reporting of screen failure participants, to meet the Consolidated Standards of Reporting Trials (CONSORT) publishing requirements, and to respond to queries from regulatory authorities. Minimal information includes date of consent, demography, screen failure details, eligibility criteria, and any serious AEs.

### 6.4.1 Retesting During Screening or Lead-In Period

Participant Re-enrollment: This study permits the re-enrollment of a participant that has discontinued the study as a pre-treatment failure (i.e., participant has not been randomized / has not been treated). If re-enrolled, the participant must be re-consented.

Retesting of laboratory parameters and/or other assessments within any single Screening or Lead-in period will be permitted (in addition to any parameters that require a confirmatory value).

The most current result prior to treatment assignment is the value by which study inclusion will be assessed, as it represents the participant's most current, clinical state.

Laboratory parameters and/or assessments that are included in Table 2-1, Screening Procedural Outline may be repeated in an effort to find all possible well-qualified participants. Consultation with the Medical Monitor may be needed to identify whether repeat testing of any particular parameter is clinically relevant.

## 7 TREATMENT

Study treatment is defined as any investigational treatment(s), marketed product(s), placebo or medical device intended to be administered to a study participant according to the study treatment allocation.

Study treatment includes both Investigational [Medicinal] Product (IP/IMP) and Non-investigational [Medicinal] Product (Non-IP/Non-IMP) and can consist of the following:

- nivolumab

- ipilimumab

An investigational product, also known as investigational medicinal product in some regions, is defined a pharmaceutical form of an active substance or placebo being tested or used as a reference in a clinical study, including products already with a marketing authorization but used or assembled (formulated or packaged) differently than the authorized form, or used for an unauthorized indication, or when used to gain further information about the authorized form.

Other medications used as support or escape medication for preventative, diagnostic, or therapeutic reasons, as components of the standard of care for a given diagnosis, may be considered as non-investigational products.

**Table 7-1: Study treatments for CA209592**

Product Description / Class and Dosage Form	Potency	IP/ Non-IMP	Blinded or Open Label	Packaging / Appearance	Storage Conditions (per label)
nivolumab/BMS -936558-01 Solution for Injection	10 mg/ml	IP	Open Label	10 mL vial containing a clear to opalescent, colorless to pale yellow liquid; may contain particulates; 5 vials/carton	Store at 2-8°C; Protect from light and freezing.
ipilimumab Solution for Injection	5 mg/ml	IP	Open Label	40mL vial containing a clear to slightly opalescent, colorless to pale yellow liquid. May contain particulates; 4 vials/carton	Store at 2-8°C; Protect from light and freezing.

## 7.1 Treatments Administered

The selection and timing of dose for each participant is as follows:

**Table 7.1-1: Selection and Timing of Dose**

Study Treatment	Unit dose strength(s)/ Dosage level(s)	Dosage formulation Frequency of Administration	Route of Administration
nivolumab + ipilimumab	240mg  1 mg/kg	Every 2 weeks  Every 6 weeks	IV  IV

### 7.1.1 Dosing Details

Participants should begin study treatment within 3 calendar days of treatment assignment in IWRS. All participants will receive nivolumab at a flat dose of 240mg as a 30 minute IV infusion, on Day 1, Day 15, and Day 29 of each treatment cycle (every 2 weeks), and ipilimumab at a dose of 1 mg/kg as a 30 minute IV infusion on Day 1 and every 6 weeks. Treatment will continue until progression, unacceptable toxicity, withdrawal of consent, the study ends, or a maximum treatment duration of 2 years, whichever occurs first.

Participants may be dosed with nivolumab no less than 12 days from the previous dose. There is no premedication recommended.

Instructions for dilution of nivolumab injection are provided in the nivolumab IB, or pharmacy manual. Care must be taken to assure sterility of the prepared solution as the product does not contain any antimicrobial preservative or bacteriostatic agent.

Instructions for dilution of ipilimumab injection are provided in the ipilimumab IB or pharmacy manual. Ipilimumab is to be administered as a 30 minute IV infusion.

Dosing calculations for ipilimumab should be based on the body weight assessed at baseline. It is not necessary to re-calculate subsequent doses if the participants' weight is within 10% of the weight used to calculate the previous dose. All doses should be rounded up or to the nearest milligram per institutional standard.

When study drugs (nivolumab and ipilimumab) are to be administered on the same day, nivolumab is to be administered first. Nivolumab infusion must be promptly followed by a saline flush to clear the line of nivolumab before starting the ipilimumab infusion. The second infusion will always be the ipilimumab study drug and will start after the infusion line has been flushed, filters changed and patient has been observed to ensure no infusion reaction has occurred. The time in between infusions is expected to be approximately 30 minutes but may be more or less depending on the situation. Separate infusion bags and filters should be used when administering nivolumab and ipilimumab on the same day. Participants should be carefully monitored for infusion reactions. If an acute infusion reaction is noted, participants should be managed according to Section 7.4.3.

Treatment with nivolumab ( $\pm$  ipilimumab) beyond initial investigator-assessed RECIST 1.1 defined progression is permitted if the participant has investigator assessed clinical benefit and is tolerating the study drugs (as specified in [Section 8.1.2](#)).

No dose modifications are allowed for nivolumab. Doses of nivolumab and/or ipilimumab may be interrupted, delayed, or discontinued depending on how well the participant tolerates the treatment. Dosing visits for nivolumab can be skipped at D15 and D29 only. For more details, see [Section 7.4.1](#) (dose delays), [Section 7.4.5](#) (resuming treatment), and [Section 8.](#) (Discontinuation).

## **7.2      Method of Treatment Assignment**

All participants will be centrally enrolled using an Interactive Response Technology (IRT). Before the study is initiated, each user will receive log in information and directions on how to access the IRT.

Study treatment will be assigned and dispensed at the study visits as listed in Schedule of Activities ([Section 2](#)).

## **7.3      Blinding**

This is an open-label study, blinding procedures are not applicable.

## **7.4      Dosage Modification**

### **7.4.1      Dose Delay Criteria**

Dose delay criteria apply to all drug-related AEs. Treatment delays are allowable up to 6 weeks for nivolumab and 12 weeks for ipilimumab from the last dose (any dose delays greater than this will require approval from the medical monitor).

Tumor assessments for all participants should continue as per protocol even if dosing is delayed.

Nivolumab and ipilimumab administration should be delayed for the following:

- Grade 2 non-skin, drug-related adverse event, with the exception of fatigue
- Grade 2 drug-related creatinine, AST, ALT and/or Total Bilirubin abnormalities
- Grade 3 skin, drug-related adverse events
- Grade 3 drug-related laboratory abnormality with the following exceptions:
  - Grade 3 lymphopenia or asymptomatic amylase or lipase does not require dose delay
  - Grade  $\geq 3$  AST, ALT, Total Bilirubin will require dose discontinuation
- Any AE, laboratory abnormality or inter-current illness which, in the judgment of the investigator, warrants delaying the dose of study medication.

Participants that have drug-related toxicities that meet the criteria for dose delay, should have both drugs (ipilimumab and nivolumab) delayed until retreatment criteria are met. (Exceptions apply to the retreatment criteria after dose delay of ipilimumab and nivolumab for Grade  $\geq 3$  amylase and lipase abnormalities that are not associated with symptoms or clinical manifestations of pancreatitis and that are attributed to ipilimumab alone.)

### **Rescheduling:**

Nivolumab may be delayed until the next planned ipilimumab dose if the next ipilimumab dose is scheduled within the next 12 days. This will permit periodic ipilimumab dosing to be synchronized with nivolumab. Dosing for nivolumab can be skipped at D15 and D29 only.

Ipilimumab should be dosed at the specified interval regardless of any delays in intervening nivolumab doses. However, in order to maintain periodic synchronized dosing of ipilimumab and nivolumab, the dosing days of nivolumab (every 2 weeks  $\pm$  3 days) and ipilimumab (every 6 weeks  $\pm$  5 days) may be adjusted within the permitted window, as long as consecutive nivolumab doses are given at least 12 days apart. Ipilimumab may be delayed beyond the 5 day window if needed to synchronize with the next nivolumab dose.

If an ipilimumab dose is delayed beyond 6 weeks from the prior ipilimumab dose, then subsequent ipilimumab doses should rescheduled to maintain the 6 week interval between consecutive ipilimumab doses.

A dose delay of ipilimumab which results in no ipilimumab dosing for  $>$  12 weeks requires ipilimumab discontinuation, with exceptions as noted in [Section 8.1.1](#).

#### **7.4.2 Dose Reductions**

There will be no dose reductions for nivolumab or ipilimumab.

#### **7.4.3 Treatment of Infusion Reactions**

Since nivolumab and ipilimumab contains only human immunoglobulin protein sequences, they are unlikely to be immunogenic and induce infusion or hypersensitivity reactions. However, if such a reaction were to occur, it might manifest with fever, chills, rigors, headache, rash, pruritus, arthralgias, hypotension, hypertension, bronchospasm, or other allergic-like reactions. All Grade 3 or 4 infusion reactions should be reported within 24 hours to the study medical monitor and reported as an SAE if it meets the criteria. Infusion reactions should be graded according to NCI CTCAE (Version 4) guidelines.

Treatment recommendations are provided below and may be modified based on local treatment standards and guidelines, as appropriate:

**For Grade 1 symptoms: (mild reaction; infusion interruption not indicated; intervention not indicated):**

- Remain at bedside and monitor subject until recovery from symptoms. The following prophylactic premedications are recommended for future infusions: diphenhydramine 50 mg (or equivalent) and/or acetaminophen/paracetamol 325 to 1000 mg at least 30 minutes before additional nivolumab or ipilimumab (as applicable) administrations.

**For Grade 2 symptoms: (moderate reaction required therapy or infusion interruption but responds promptly to symptomatic treatment (eg, antihistamines, non-steroidal anti-inflammatory drugs, narcotics, corticosteroids, bronchodilators, IV fluids); prophylactic medications indicated for  $\leq$  24 hours):**

- Stop the nivolumab infusion, begin an IV infusion of normal saline, and treat the subject with diphenhydramine 50 mg IV (or equivalent) and/or acetaminophen/paracetamol 325 to 1000 mg; remain at bedside and monitor subject until resolution of symptoms. Corticosteroid and/or bronchodilator therapy may also be administered as appropriate. If the infusion is interrupted, then restart the infusion at 50% of the original infusion rate when symptoms resolve; if no further complications ensue after 30 minutes, the rate may be increased to 100% of the original infusion rate. Monitor subject closely. If symptoms recur, then no further nivolumab or ipilimumab (as applicable) will be administered at that visit.
- For future infusions, the following prophylactic premedications are recommended: diphenhydramine 50 mg (or equivalent) and/or acetaminophen/paracetamol 325 to 1000 mg should be administered at least 30 minutes before nivolumab or ipilimumab (as applicable) infusions. If necessary, corticosteroids (up to 25 mg of hydrocortisone or equivalent) may be used.

**For Grade 3 or 4 symptoms: (severe reaction, Grade 3: prolonged [ie, not rapidly responsive to symptomatic medication and/or brief interruption of infusion]; recurrence of symptoms following initial improvement; hospitalization indicated for other clinical sequelae (eg, renal impairment, pulmonary infiltrates). Grade 4: Life-threatening; pressor or ventilatory support indicated):**

- Immediately discontinue infusion. Begin an IV infusion of normal saline and treat the subject as follows: Recommend bronchodilators, epinephrine 0.2 to 1 mg of a 1:1000 solution for subcutaneous administration or 0.1 to 0.25 mg of a 1:10,000 solution injected slowly for IV administration, and/or diphenhydramine 50 mg IV with methylprednisolone 100 mg IV (or equivalent), as needed. Subject should be monitored until the Investigator is comfortable that the symptoms will not recur. Nivolumab or ipilimumab (as applicable) will be permanently discontinued. Investigators should follow their institutional guidelines for the treatment of anaphylaxis. Remain at bedside and monitor subject until recovery of the symptoms.

In case of late-occurring hypersensitivity symptoms (eg, appearance of a localized or generalized pruritus within 1 week after treatment), symptomatic treatment may be given (eg, oral antihistamine or corticosteroids).

#### **7.4.4 Management Algorithms for Immuno-Oncology Agents**

Immuno-oncology (I-O) agents are associated with AEs that can differ in severity and duration than AEs caused by other therapeutic classes. Nivolumab and ipilimumab are considered immuno-oncology agents in this protocol. Early recognition and management of AEs associated with immuno-oncology agents may mitigate severe toxicity. Management Algorithms have been developed to assist investigators in assessing and managing the following groups of AEs:

- Gastrointestinal
- Renal
- Pulmonary
- Hepatic
- Endocrinopathy

- Skin
- Neurological
- Myocarditis

The above algorithms are found in both the nivolumab and ipilimumab Investigator Brochures, as well as in [Appendix 7](#).

#### **7.4.5 Criteria to resume dosing**

##### **7.4.5.1 Criteria to resume nivolumab dosing**

Participants may resume treatment with nivolumab when the drug-related AE(s) resolve(s) to Grade  $\leq 1$  or baseline, with the following exceptions:

- Subjects may resume treatment in the presence of Grade 2 fatigue
- Subjects who have not experienced a Grade 3 drug-related skin AE may resume treatment in the presence of Grade 2 skin toxicity
- For subjects with Grade 2 AST, ALT, or Total bilirubine elevations, dosing may resume when laboratory values return to baseline and management with corticosteroids, if needed, is complete.
- Subjects with combined Grade 2 AST/ALT AND total bilirubin values meeting discontinuation parameters ([Section 8.1.1](#)) should have treatment permanently discontinued.
- Drug-related pulmonary toxicity, diarrhea or colitis must have resolved to baseline before treatment is resumed. Subjects with persistent Grade 1 pneumonitis after completion of a steroid taper over at least 1 month may be eligible for retreatment if discussed with and approved by BMS Medical Monitor.
- Subjects with Grade 1-3 drug-related endocrinopathies adequately controlled with only physiologic hormone replacement may resume treatment after consultation with the BMS Medical Monitor.
- Participants who received systemic corticosteroids for management of any drug-related toxicity must be off corticosteroids or have tapered down to an equivalent dose of prednisone  $\leq 10$  mg/day.
- Participants who delay study treatment due to any Grade  $\geq 3$  amylase or lipase abnormality that is not associated with symptoms or clinical manifestations of pancreatitis, and that is assessed by the investigator to be related to ipilimumab and not to nivolumab, may resume nivolumab when the amylase or lipase abnormality has resolved to Grade  $< 3$ . The BMS Medical Monitor should be consulted prior to resuming nivolumab in such participants.
- Dose delay of nivolumab which results in treatment interruption of  $> 6$  weeks requires treatment discontinuation, with exceptions as noted in [Section 8.1.1](#).

One exception to note is when ipilimumab and nivolumab doses are delayed due to drug-related Grade  $\geq 3$  amylase or lipase abnormalities not associated with symptoms or clinical manifestations of pancreatitis. If the investigator assesses the Grade  $\geq 3$  amylase or lipase abnormality to be related to ipilimumab and not related to nivolumab, nivolumab may be resumed when the amylase or lipase abnormality resolves to Grade  $< 3$  but ipilimumab may only be resumed when the amylase

or lipase abnormality resolves to Grade 1 or baseline. Investigator attribution of this toxicity to the ipilimumab dosing must be clearly noted in the participant's medical chart. The BMS Medical Monitor should be consulted prior to resuming nivolumab in such participants.

See [Section 8](#) for treatment discontinuation criteria.

#### **7.4.5.2 Criteria to resume ipilimumab dosing**

Participants may resume treatment with ipilimumab when drug-related AE(s) resolve(s) to Grade 1 or baseline value, with the following exceptions:

- Participants may resume treatment in the presence of Grade 2 fatigue.
- Participants who have not experienced a Grade 3 drug-related skin AE may resume treatment in the presence of Grade 2 skin toxicity.
- Participants with baseline Grade 1 AST/ALT or total bilirubin elevations who require dose delays for reasons other than a 2-grade shift in AST/ALT or total bilirubin may resume treatment in the presence of Grade 2 AST/ALT or total bilirubin.
- Participants with combined Grade 2 AST/ALT and total bilirubin values meeting discontinuation parameters ([Section 8.1.1](#)) should have treatment permanently discontinued.
- Drug-related pulmonary toxicity, diarrhea or colitis must have resolved to baseline before treatment is resumed. Subjects with persistent Grade 1 pneumonitis after completion of a steroid taper over at least 1 month may be eligible for retreatment if discussed with and approved by BMS Medical Monitor.
- Participants who received systemic corticosteroids for management of any drug-related toxicity must be off corticosteroids or have tapered down to an equivalent dose of prednisone  $\leq 10$  mg/day.
- Subjects with Grade 1-3 drug-related endocrinopathies adequately controlled with only physiologic hormone replacement may resume treatment after consultation with the BMS Medical Monitor.
- Dose delay of ipilimumab which results in no ipilimumab dosing for  $> 12$  weeks requires ipilimumab discontinuation, with exceptions as noted in [Section 8.1.1](#). Although there is overlap among the discontinuation criteria, if discontinuation criteria are met for ipilimumab, but not for nivolumab, treatment with nivolumab may continue if ipilimumab is discontinued.

Ipilimumab may not be resumed sooner than 6 weeks ( $\pm 5$  days) after the prior ipilimumab dose.

In general, participants who meet criteria to resume ipilimumab will also have met criteria to resume nivolumab, so it should be feasible to synchronize dosing of both drugs when resuming ipilimumab. In order to facilitate this, the dosing days of nivolumab and ipilimumab may be adjusted within the permitted  $\pm 5$  day window, as long as consecutive nivolumab doses are given at least 12 days apart.

One exception to note is when ipilimumab and nivolumab doses are delayed due to drug-related Grade  $\geq 3$  amylase or lipase abnormalities not associated with symptoms or clinical manifestations of pancreatitis. If the investigator assesses the Grade  $\geq 3$  amylase or lipase abnormality to be related to ipilimumab and not related to nivolumab, nivolumab may be resumed when the amylase or lipase abnormality resolves to Grade  $< 3$  but ipilimumab may only be resumed when the amylase

or lipase abnormality resolves to Grade 1 or baseline. Investigator attribution of this toxicity to the ipilimumab dosing must be clearly noted in the participant's medical chart. The BMS Medical Monitor should be consulted prior to resuming nivolumab in such participants.

See [Section 8](#) for treatment discontinuation criteria.

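### For participants with Grade 1 AST/ALT or bilirubin at baseline, the protocol lets ipilimumab resume at a drug-related Grade 2 value that also requires both drugs to be delayed

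*Combined protocol and SAP*

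**What the plan says.** Four sections of the protocol govern a Grade 2 liver test.

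- **Section 7.4.1 (delay).** The triggers include "Grade 2 drug-related creatinine, AST, ALT and/or Total Bilirubin abnormalities". Participants whose drug-related toxicity meets a trigger "should have both drugs (ipilimumab and nivolumab) delayed until retreatment criteria are met". No liver-test exception is made for participants who start at Grade 1. At Grade 3 or above, "AST, ALT, Total Bilirubin will require dose discontinuation".
- **Section 7.4.5.1 (resuming nivolumab).** After a Grade 2 AST, ALT or bilirubin elevation, "dosing may resume when laboratory values return to baseline and management with corticosteroids, if needed, is complete". Again nothing is said about baseline Grade 1.
- **Section 7.4.5.2 (resuming ipilimumab).** The general rule is "Participants may resume treatment with ipilimumab when drug-related AE(s) resolve(s) to Grade 1 or baseline value". One of its exceptions is for a Grade 1 baseline in either liver measure where the delay was not caused by a 2-grade shift; the people it covers "may resume treatment in the presence of Grade 2 AST/ALT or total bilirubin". The section later says that, in general, "participants who meet criteria to resume ipilimumab will also have met criteria to resume nivolumab".
- **Section 8.1.1 (discontinuation).** Drug-related Grade 3 or higher AST, ALT or bilirubin requires discontinuation. For Grade 3 AST or ALT, continuation can be discussed with the Medical Monitor if the investigator sees a favorable balance. Ipilimumab may not continue once nivolumab has been discontinued.

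**The concern.** A site treating a participant with a Grade 1 baseline and a drug-related Grade 2 value finds one section permitting ipilimumab and another requiring both drugs to be delayed at that same value. Following the permission would mean giving ipilimumab while the nivolumab rule still holds nivolumab. Sites could reasonably act differently, and Section 9 rules out waivers, so there is no agreed way around the difficulty.

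Liver toxicity is among the risks of the combination named in Section 3.3. What is at stake is safety, and consistency across sites in which drugs a participant receives and what counts as a deviation. No sample size, interval width or endpoint definition depends on it.

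**Working it through.** The plan states no figure to reproduce and no arithmetic decides the point. The check applies the four sections, case by case, to a drug-related AST, ALT or bilirubin elevation.

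1. **Baseline Grade 1, now Grade 2; the liver test is the reason for delay.** The rise is one grade, so the delay is for a reason other than a 2-grade shift.
   - 7.4.1: delay both drugs.
   - 7.4.5.1: hold nivolumab until return to baseline.
   - 7.4.5.2: ipilimumab may resume at Grade 2.
   - Result: conflict.
2. **Baseline Grade 1, delayed for another toxicity, liver test now at drug-related Grade 2.**
   - 7.4.5.2: ipilimumab may resume as far as the liver test is concerned.
   - 7.4.1: the same value is itself a delay trigger for both drugs.
   - 7.4.5.1: nivolumab waits for return to baseline.
   - Result: conflict.
3. **Baseline Grade 1, 2-grade shift.** Grade 1 plus 2 grades is Grade 3. Sections 7.4.1 and 8.1.1 treat this as discontinuation, apart from the Medical Monitor discussion for AST or ALT. The condition that limits the exception therefore corresponds to no liver-test delay trigger in 7.4.1, where the delay grade is 2.
4. **Baseline normal, now Grade 2.** The exception does not apply. Ipilimumab waits for Grade 1 or baseline and nivolumab for baseline. There is no conflict at Grade 2. A smaller mismatch remains at Grade 1, where ipilimumab may resume and nivolumab may not.

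**Can such participants be enrolled?** Exclusions 3f to 3h in Section 6.2 bar AST or ALT above 3.0 x ULN and total bilirubin above 1.5 x ULN, with a separate limit for Gilbert syndrome. Values above normal but within those limits are admitted. The protocol grades by CTCAE version 4 without reproducing the boundaries; I take mild elevations of this kind to be Grade 1.

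**Interaction with the timing rules.** Ipilimumab may not resume sooner than 6 weeks (plus or minus 5 days) after its prior dose: 42 days, with a window of 37 to 47. A nivolumab interruption beyond 6 weeks (42 days) requires its discontinuation, subject to the exceptions in 8.1.1, and ipilimumab may not then continue. If both drugs were last given on Day 1, nivolumab reaches its limit at about the time ipilimumab becomes eligible. If nivolumab was last given on Day 29, 28 days later, ipilimumab becomes eligible around 42 - 28 = 14 days into the nivolumab interruption, leaving 28 days in which ipilimumab could be given with nivolumab held.

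**The case against.** The best defence is that the rules are drug-specific by design. Section 7.4.1 delays dosing only until retreatment criteria are met, so it hands over to 7.4.5, which sets separate criteria for each drug. A specific resumption exception can be read as ending the delay for that drug, and no section says outright that a restart at Grade 2 triggers a new delay. The protocol accepts elsewhere that the drugs can separate: Section 7.4.1 has ipilimumab given on schedule despite intervening nivolumab delays, and 8.1.1 bars ipilimumab only after nivolumab is discontinued, not while it is delayed. The exception is also permissive: the investigator may still delay or stop, and combined AST/ALT and bilirubin elevations meeting 8.1.1 lead to permanent discontinuation.

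This makes separate criteria legitimate, but does not remove the conflict. A participant restarted at drug-related Grade 2 still meets the 7.4.1 trigger as worded. Where the sponsor meant retreatment to diverge by drug for a laboratory abnormality, for amylase and lipase, it flagged the divergence in 7.4.1 and in both resumption sections and added attribution and Medical Monitor consultation. The liver-test divergence has none of this, and runs the other way, with ipilimumab first.

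Three stronger readings are tempting and not supported:

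- That any participant may restart ipilimumab at Grade 2. The general rule in 7.4.5.2 excludes this for normal baselines, and the 7.4.1 liver-test trigger covers drug-related elevations only.
- That 7.4.5.2 flatly contradicts its own statement on meeting both sets of criteria. That statement is qualified as holding in general; the exception fits poorly with it, and no more can be said.
- That the whole protocol leaves the matter open. The hepatic algorithm in Appendix 7 is a figure not available in the text reviewed, so what it says about Grade 2 could not be checked.

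**Conclusion.** The point holds for participants with baseline Grade 1 AST/ALT or total bilirubin and a drug-related Grade 2 value. For them, Section 7.4.5.2 permits ipilimumab where 7.4.1 delays both drugs and 7.4.5.1 holds nivolumab, and the condition attached to the permission does not match the delay triggers in 7.4.1.

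It is a minor internal inconsistency with a bearing on safety. Its frequency cannot be estimated: the documents give neither the share with Grade 1 at baseline nor the share of those reaching drug-related Grade 2. The only ceiling is the number with Grade 1 at baseline among about 250 treated (100 in Part 1 plus 150 in Part 2). The conclusion rests on the text of the four sections and on mild baseline elevations within the exclusion limits being Grade 1. No view is taken on which rule is clinically right.

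**What to change.** Reconcile Sections 7.4.1, 7.4.5.1, 7.4.5.2 and 8.1.1 for drug-related Grade 2 AST, ALT and total bilirubin. The revised text should state, for each drug, how participants with Grade 1 at baseline are handled. It should also say what the 2-grade-shift condition refers to, given how Grade 3 is treated, and whether a Grade 2 value at which a drug has been resumed counts as a new delay trigger. The sponsor should check the hepatic algorithm in Appendix 7 against the result. The criteria need not be the same for both drugs; they need to be compatible. The sponsor's clinical team decides the rule.

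The cost is a wording change at the next amendment and a notice to sites, with no effect on sample size or the planned analyses.
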